13. STATISTICAL CONSIDERATIONS

This is a one arm phase II trial. The primary endpoint is 1-year disease-free survival (DFS) from point of salvage surgery. A 1-year DFS of 57% [36, 39-41] is the basis of the null hypothesis. Based on a 1-year DFS of 57%, the hazard is .5621 DFS events/person-year of follow up. A 30% reduction in that hazard would lead to a hazard of .3935. When 37 DFS events are observed among n=54 patients who receive salvage surgery and begin adjuvant treatment, this design has 81% power to detect a 30% reduction in the DFS hazard (using a one-sided 10% type I error rate, Wald's test). Assuming an exponential distribution, this corresponds to improving 1-year DFS from 57% to approximately 67.5% from using the adjuvant treatment.

Allowing for patients who may fail prior to salvage surgery, not receive the adjuvant portion of treatment, or for patients who are declared ineligible, n=58 patients will be registered to the trial.

The primary efficacy population includes all eligible patients who receive salvage surgery and begin adjuvant treatment. The Kaplan-Meier method will be used to estimate time-to-event endpoints.

For secondary objectives: Best overall response (at the end of the window phase of the trial) will be summarized as a proportion with a corresponding exact 95% confidence interval (CI) (noting that a 'modified' version (no confirmation of initial CR or PR) of RECIST will be used for patients whose disease initially achieves a CR or PR: the patients' tumor will be resected prior to confirming the CR or PR at least 4 weeks after initial response). Adverse events will be classified and graded according to the CTCAE v.4.0. Frequencies of adverse events will be summarized. The distributions of n-year DFS and survival will be estimated using a Kaplan-Meier method with corresponding 95% confidence intervals for time-specific event time. Several correlative studies are also planned. Given the small sample size of this trial, these studies are exploratory. Samples will be collected at baseline and at post-baseline timepoints as outlined in the protocol. Markers from the samples (cluster differentiation markers from both tumor and circulating peripheral blood, see Section 9.1) will be summarized descriptively and graphically. Within subject changes in markers will also be analyzed. Assuming n=50 patients with useable baseline and post baseline markers, there is 81% power to detect .42 SD mean difference (Wilcoxon sign rank test two-sided 0.05 alpha level).

The following stopping rule will be used to monitor delays in salvage surgery due to excessive nivolumab and/or lirilumab-related toxicity: if 3 or more of the first 10 patients who begin protocol treatment experience treatment related toxicities which cause delays in definitive surgery, accrual to the trial will be suspended to further evaluate the events and decisions made regarding the overall status of the trial. If the true delay in surgery rate due to toxicity is 10% then the probability of suspending accrual is 7%; if the true rate is 20%, then the probability of suspending accrual is 32.2%; if the true delay in surgery rate due to toxicity is 30% then the probability of suspending accrual is 62%. Adverse events will be continuously monitored

throughout the trial by the study team with decisions made accordingly regarding the study status and patient entry throughout the duration of the trial.

Assuming accrual of approximately 2.2 patients per month, 2 years of accrual and 2 years of follow up are needed for the operating characteristics for the primary endpoint. Analysis of primary endpoint is estimated to take place therefore approximately 4 years after the trial opens to accrual (approximately 2 years of accrual and 2 years follow up) or when 38 DFS events have been observed. Due to possible delays in initiation of approval at other sites, in initiation of accrual itself, the accrual period could take longer and due to possible delays in data submission and processing, the actual analysis time for the primary endpoint could be later. Analysis of secondary endpoints will require more follow-up. Assuming that the stated accrual assumptions hold, if at any time within 4 years >37 DFS events are observed, the study will not have met its primary endpoint.

See also Data Sharing Agreement in section 12.

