2. BACKGROUND

2.1 Study Disease(s)

Locoregional recurrence is a major cause of death in patients with squamous cell carcinoma of the head and neck (SCCHN), affecting up to 50% of patients treated with definitive therapy, which may include upfront surgical resection followed by adjuvant therapy or concurrent chemoradiotherapy [1]. Survival outcomes are generally poor for patients with locoregionally

recurrent disease and therapeutic options are limited by prior treatments (radiation and/or chemotherapy) [2]. When possible, salvage surgery is considered in these patients and frequently represents their only remaining chance at possible cure or long-term survival. Retrospective historical data have estimated 3-year overall survival (OS) at 37% among all surgically salvaged, recurrent SCCHN patients [3], with variability based on primary site of disease and interval of disease recurrence [4]. In a prospective single-institution observational cohort of 109 patients who underwent surgical salvage, 2-year disease-free survival (DFS) was 44% for all patients and correlated with stage (stage I, II 67-73%; stage III, IV 22-33%; $p = 0.0005$) and by site of recurrent disease (pharynx: 28%, oral cavity 47%, larynx: 58%, neck: 25%; $p = 0.0645$) [3]. Aside from salvage surgery or reirradiation in select patients, therapeutic options are limited and the standard of care is active surveillance following any salvage approach. A trial of 130 patients with locoregionally recurrent, operable SCCHN randomized patients to receive full-dose reirradiation and concurrent chemotherapy vs. active surveillance following re-resection and demonstrated improved rates of locoregional control (16 vs. 32 events, HR 2.73, 95% CI 1.66-4.51, $p < 0.0001$) in the reirradiation arm but without an improvement in OS ($p = 0.50$) [5] – with an increase in acute and late toxicities observed in the chemoradiotherapy arm. Given these considerations, there is an urgent need to evaluate additional therapies in this critical population.

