an important consideration, the site of disease recurrence often dictates available retreatment options and prognosis: laryngeal recurrence can sometimes be salvaged with total laryngectomy (5-year OS approaches 60%) as compared with oropharyngeal or hypopharyngeal tumors (5-year OS in the 16-44% range) which are more difficult to resect [36]. Post-salvage positive resection margins and extracapsular spread of disease also have been reported as predictors of poor outcome [37]. Patient-specific factors also play heavily into decision-making, as prior therapy may have contributed to poor cardiopulmonary or renal reserve, cognitive issues, tobacco and alcohol exposure may be ongoing, and there remain significant quality of life concerns with re-resection. While the morbidity associated with salvage surgery can be substantial depending on the site and extent of disease, it often represents the best therapeutic option for operable patients [38]. For the above reasons, capturing outcomes in this heterogeneous population can be difficult. In a single-center retrospective series of 109 patients undergoing salvage surgery for recurrent SCCHN, 5-year OS was 42% compared with a 5-year DFS of 47% for all patients [36]. Accounting for specific disease sites, 3-year OS in surgically salvaged oropharyngeal tumors has been estimated at 48.7% [39], whereas 5-year OS in laryngeal and hypopharyngeal recurrence treated with surgical salvage is 27-57% [40, 41]. A large multicenter meta-analysis that included over 1000 patients reported a 5-year OS of 39%. Of note, these studies included patients receiving salvage surgery with or without additional ‘adjuvant’ chemotherapy and/or radiation—the benefit of which remains controversial. Investigating alternative therapeutic strategies that incorporate novel treatment mechanisms is warranted.

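### The primary test applies a constant hazard derived from 1-year DFS to 2-4 years of follow-up; if risk falls after year 1, its false-positive rate is far above the stated 10%

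*Combined protocol and SAP*

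**What the plan says.** Section 13 names 1-year DFS from salvage surgery as the primary endpoint. On the null it states: "A 1-year DFS of 57% [36, 39-41] is the basis of the null hypothesis". It converts this to a rate: "Based on a 1-year DFS of 57%, the hazard is .5621 DFS events/person-year of follow up". For the alternative: "A 30% reduction in that hazard would lead to a hazard of .3935". The sizing sentence begins "When 37 DFS events are observed among n=54 patients who receive salvage surgery and begin adjuvant treatment" and claims "81% power to detect a 30% reduction in the DFS hazard (using a one-sided 10% type I error rate, Wald's test". An exponential distribution is stated as an assumption.

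On timing, Section 13 says that "2 years of accrual and 2 years of follow up are needed for the operating characteristics for the primary endpoint", so each patient contributes between 2 and 4 years. It adds that more than 37 DFS events at any time within 4 years means the primary endpoint has not been met. Kaplan-Meier is named for estimation, with 95% intervals at specific times.

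The background gives later outcomes after salvage surgery. Section 2.1 reports that "2-year disease-free survival (DFS) was 44% for all patients" in a cohort of 109, and cites a 3-year OS of 37%. Section 2.4 reports that "5-year OS was 42% compared with a 5-year DFS of 47% for all patients [36" (reference 36 there), and a meta-analysis with 5-year OS of 39%. No section discusses a non-constant hazard, gives a null value beyond 1 year, or plans a check of the exponential assumption.

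**The concern.** The endpoint is DFS at 12 months, but the test pools events and person-time out to 4 years. The 57% fixes the null only over the first year; after that the null rests on the exponential assumption alone. If recurrence after salvage surgery is concentrated early, later person-time carries fewer events than .5621 per year whatever the treatment does. The pooled rate then drops below the null with no drug effect. In a single-arm trial the null is the only comparator, so ordinary flattening of the curve would be credited to nivolumab plus lirilumab.

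**Working it through.** **1. Reproduce the plan's figures.** Null hazard: -ln(0.57) = 0.5621. Alternative: 0.7 × 0.5621 = 0.3935, and exp(-0.3935) = 67.5% at 1 year. Power of a one-sample Wald test on the log exponential hazard: Φ(√37 × |ln 0.70| - 1.2816) = 81.3%, which matches the stated 81%. A two-arm formula gives 42%, so the pooled one-sample hazard test is the one that was sized. With 54 patients, uniform 2-year accrual and 2 more years of follow-up, expected events are 37.0 under the alternative and 43.5 under the null.

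**2. What the constant null implies.** 0.57² = 32.5% DFS at 2 years, 0.57³ = 18.5% at 3 years, 0.57⁵ = 6.0% at 5 years.

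**3. Compare with the background.** If 57% at 1 year and 44% at 2 years lay on one curve, the year-2 hazard would be ln(0.57/0.44) = 0.259, less than half the null. The average over 2 years would be -ln(0.44)/2 = 0.4105. That is 0.73 × 0.5621, already close to the 0.3935 the regimen is meant to achieve.

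**4. Pass rate with no treatment effect.** Simulated trials: 54 patients, accrual as above, analysis at 4 years, passing if (ln(events/person-years) - ln 0.5621) × √events < -1.2816. Every curve has 57% DFS at 1 year. The shapes after year 1 are assumptions.

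| DFS curve, no effect | Wald test passes | 37 or fewer events by 4 years |
|---|---|---|
| Constant hazard 0.5621 | 9% | 2% |
| 44% at 2 y, year-2 hazard continued | 76% | 72% |
| 44% at 2 y, 37% at 3 y, then continued | 83% | 84% |
| 44% at 2 y, 42% at 5 y | 93% | 97% |
| 40% at 2 y, 33% at 3 y | 67% | |
| 36% at 2 y, 30% at 3 y | 51% | |
| 40% at 2 y, 28% at 3 y | 49% | |
| 38% at 2 y, 27% at 3 y | 43% | |
| 35% at 2 y, 25% at 3 y | 30% | |
| 33% at 2 y, 22% at 3 y | 18% | |
| 33% at 2 y, year-2 hazard continued | 10% | 3% |
| 28% at 2 y, year-2 hazard continued | 1% | 0.2% |

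Other shapes through 57% and 44% move the result little: a Weibull curve gives 73%, and a curve flat after year 2 gives 94%. Analysing at 37 events or 4 years, whichever comes first, changes the results for curves through 44% by about 4 points or less.

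**5. Sampling error in the 44%.** Treating it as a simple proportion of 109 (an assumption), the 95% interval is 0.44 ± 1.96 × √(0.44 × 0.56/109), or 35% to 53%. With Weibull curves the pass rate is 19% at 35%, about 50% at 40% and 96% at 53%.

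**6. Tests confined to year 1.** With person-time ended at 12 months the rejection rate is about 9%, both under the constant null and under a curve flat after year 2. Expected events under the target are 54 × (1 - 0.675) = 17.6 and power is about 60%. A 1-year Kaplan-Meier test against 57% rejects in about 9.5-10% under these curves, with about 61% power.

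**The case against.** The strongest reply is that no documented series shows 57% flattening to 44%. The 57% is credited to references 36 and 39-41 and the 44% to reference 3, so joining them is a splice. Taken together, the background figures are not even a coherent survival curve: 44% DFS at 2 years but 47% at 5, and 37% OS at 3 years but 39-42% at 5. This stands. A reader might infer that the protocol's history demonstrates slowing failure after year 1; the documents suggest it but do not show it.

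Definitions also differ. Section 11.1.6 counts any death and non-head-and-neck second primaries as DFS events. A 5-year DFS of 47% above an OS of 42% in the same series is impossible on that definition, so the 47% is not used in the table. How the 44% was defined is not stated. OS is only a ceiling, so the curves that reach 37% or 42% lean towards high pass rates. If later DFS followed the stage III/IV figures in Section 2.1 (22-33% at 2 years), the pass rate would be about 10% or less, although 57% at 1 year would then be a doubtful null for that case mix. Some historical patients had adjuvant chemotherapy or radiation, which Section 5.2 excludes here, so the history is not purely untreated.

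Finally, the exponential assumption is declared, and the planned 1-year Kaplan-Meier estimate can be set beside 57% unaffected by later flattening. It would therefore be too strong to infer that a positive trial would be uninformative. But that estimate is not the sized test: the stated error rate, power, event target and timing all belong to the multi-year hazard test.

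**Conclusion.** The concern holds in conditional form. The stated 10% error rate depends on a constant hazard beyond year 1 that the protocol does not justify and that its own background figures call into question. If 57% at 1 year and 44% at 2 years are both roughly right for this population, an ineffective regimen passes in about 75-93% of trials. For lower assumed curves with 2-year DFS of 33-40% the rate is about 18-67%. It is near nominal only if 2-year DFS is close to 32%, and the test is conservative below that. The 37-event rule shifts in the same direction.

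A reader might infer a demonstrated false-positive rate of 80-90%. The documents do not support that precision: it needs the cross-series pairing and later points borrowed from OS. What they do support is that the error rate is uncontrolled over a wide range, mostly well above 10%. The results assume 54 patients, uniform accrual and the pooled hazard test that reproduces the stated power.

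**What to change.** Make the formal test match the 1-year endpoint. Either end person-time for the hazard test at 12 months, or test the 1-year Kaplan-Meier estimate against 57%. Then restate the power (about 60% with 54 patients, not 81%), the event target, the analysis time and the rule on more than 37 events.

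Alternatively, keep the longer follow-up and use a one-sample log-rank test whose expected events come from a justified historical cumulative hazard. On an assumed curve of 57%, 44% and 37% at 1, 2 and 3 years this holds the error at about 9%, with about 74% power for a 30% hazard reduction and about 27 expected events at 4 years under the target. The reference curve would be pieced together from different series, and the error control depends on it: if the true curve flattens to 42% at 5 years, rejection with no effect rises to about 25%. Sensitivity to the reference curve should be shown.

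Either route changes only Section 13 and its calculations, with no added patients, visits or data. The cost is lower stated power. Keeping 37 events within a 12-month test would need about 37/0.325 = 114 patients, so the sponsor should state openly which power it accepts.

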1. OBJECTIVES

1.1 Study Design

This is a phase II, open label, non-randomized, multi-institutional study of nivolumab (anti-PD-1) and lirilumab (anti-KIR) in patients with relapsed, resectable, squamous cell carcinoma of the head and neck (SCCHN). Approximately 58 patients with confirmed locoregionally recurrent squamous cell carcinoma of the head and neck (including any primary site), who are candidates for salvage surgery will be enrolled in this study. A single dose of both study drugs will be given during a window of opportunity phase, before salvage surgery, followed by treatment with both study drugs in the adjuvant setting. Treatment in the adjuvant phase will continue for a maximum of 6 cycles or until disease progression or recurrence. The aim of this study is to improve disease-free survival in this critical SCCHN population. Primary endpoint is to evaluate disease-free survival at 1-year from the time of salvage surgery. Secondary endpoints will include disease-free survival at 2-years, and overall survival at 3-years.

The window phase of this study (from biopsy to surgical salvage) would allow administration of initial doses of immune checkpoint inhibitors facilitating assessment of toxicity and evaluation of early radiologic and clinicopathologic response, as well as immune and molecular correlates.

We hypothesize that the combination of nivolumab and lirilumab used as adjuvant therapy in patients with locoregionally recurrent, resectable SCCHN will improve 1-year disease-free survival compared with standard observation in this high-risk population.

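### Section 13 names 1-year DFS as the primary endpoint but gives it no test or power of its own; success is decided on the DFS hazard over full follow-up and on an event-count rule that does not match the stated 10% and 81%.

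*Combined protocol and SAP*

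**What the plan says.** Section 1.1 states: "Primary endpoint is to evaluate disease-free survival at 1-year from the time of salvage surgery". Section 1.2 makes the primary objective the estimation of that quantity, and section 13 repeats: "The primary endpoint is 1-year disease-free survival (DFS) from point of salvage surgery". The reference value is also a 1-year figure: "A 1-year DFS of 57% [36, 39-41] is the basis of the null hypothesis".

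The powered hypothesis is on another scale. Section 13 converts 57% to a hazard of .5621 per person-year, sets the alternative at .3935, and says that with 37 events among 54 patients "this design has 81% power to detect a 30% reduction in the DFS hazard", using a one-sided 10% Wald test. The link back to 1 year is "Assuming an exponential distribution, this corresponds to improving 1-year DFS from 57% to approximately 67.5% from using the adjuvant treatment".

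On timing, "2 years of accrual and 2 years of follow up are needed for the operating characteristics for the primary endpoint". Section 13 adds that, if accrual goes as assumed, "if at any time within 4 years >37 DFS events are observed, the study will not have met its primary endpoint".

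Kaplan-Meier estimation is planned for the time-to-event endpoints, and the paragraph on secondary objectives adds: "The distributions of n-year DFS and survival will be estimated using a Kaplan-Meier method", with 95% confidence intervals. No critical value, test or power is attached to the 1-year estimate.

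**The concern.** The named endpoint is disease-free status at one year. Both rules that decide success use every event over 2 to 4 years per patient. Later events bear on 1-year DFS only through the assumption that the hazard stays constant.

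If the hazard falls after year 1, the trial could be declared positive although 1-year DFS is exactly the null 57%. If an early benefit fades, it could be declared negative although 1-year DFS is 67.5%. In a single-arm trial judged against a fixed historical figure, this determines what a positive result means. The event-count rule raises a second question: whether it has the same error rate and power as the Wald test beside it.

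**Working it through.** **Inputs from section 13:** null 1-year DFS 0.57; hazards .5621 and .3935; 37 events; n = 54; one-sided 10% (z = 1.2816); 2 years of accrual plus 2 years of follow-up. **Assumed here:** uniform accrual, no losses, analysis at 4 years.

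1. **The plan's own figures.** −ln 0.57 = .5621; .5621 × 0.7 = .3935; exp(−.3935) = 0.6747. Power = Φ(−ln 0.7 × √37 − 1.2816) = Φ(0.3567 × 6.083 − 1.2816) = Φ(0.888) = 81.3%. The probability of an event by the analysis is 1 − [exp(−2λ) − exp(−4λ)]/(2λ). This is 0.6849 at .3935 (37.0 events expected in 54) and 0.8049 at .5621 (43.5 events). The 81%, the 37 and the 67.5% all reproduce.

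2. **Share of events in year 1 under the alternative.** 54 × (1 − 0.6747) = 17.6, and 17.6/37 is about 47%.

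3. **Direct test of 1-year DFS, complete follow-up to 1 year.** Exact binomial, n = 54: P(X ≥ 35 | 0.57) = 15.3% and P(X ≥ 36 | 0.57) = 9.6%, so the test rejects from 36. P(X ≥ 36 | 0.6747) = 61.3%. Normal approximations run from 58% to 69%: complementary log-log 58–64%, null variance 61%, own variance 64%, log 69%. Applied as tests, all these scales first reject at 36 of 54, the log scale only narrowly (z at 35 is 1.2814). The exact power is therefore 61% for each. Power reaches 80% at a true 1-year DFS of about 71%.

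4. **Constant hazard against the background.** From 57% at 1 year, a constant hazard implies 0.57² = 32% at 2 years and 0.57⁵ = 6% at 5 years. Section 2.1 reports 44% at 2 years in a prospective cohort, but that cohort is not a cited source for the 57%; taken alone, 44% fits a constant hazard with √0.44 = 66% at 1 year. Section 2.4 reports 47% at 5 years in a retrospective series that is a source for the 57%. Its OS is 42%, below its DFS, so its DFS cannot follow section 11.1.6, which counts every death as an event.

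5. **Planned Wald test when the hazard changes after year 1.** Simulation, 200,000 trials per row. Year-2 hazards are ln(0.57/0.36) = .4595, ln(0.57/0.40) = .3542 and ln(0.57/0.44) = .2589, continued thereafter. The non-constant rows are assumptions, not estimates from the documents.

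| Assumed truth | Wald test succeeds | Direct 1-year test succeeds |
|---|---|---|
| Constant .5621 (null) | 9.0% | 9.6% |
| Constant .3935 (alternative) | 82.5% | 61.2% |
| 57% at 1 year, 36% at 2 | 24.2% | 9.6% |
| 57% at 1 year, 40% at 2 | 50.2% | 9.6% |
| 57% at 1 year, 44% at 2 | 75.7% | 9.7% |
| 67.5% at 1 year, then .5621 | 40.1% | 61.3% |

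6. **Event-count rule under the plan's own exponential assumptions.** P(≤ 37 events of 54 by 4 years) is 2.5% with event probability 0.8049 and 55.3% with 0.6849. The cut-off equals the expected count under the alternative, so an effective treatment passes only slightly more than half the time. Requiring both the Wald test and ≤ 37 events gives 2.4% and 55.1%.

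**The case against.** The best defence is that the plan is open about what it does. The 81% is attached to the hazard, the exponential assumption stands in the sentence that makes the conversion, and the primary objective is to estimate 1-year DFS, for which Kaplan-Meier is planned. All of that stands. A reader who inferred that the endpoint has no analysis, or that the 81% is a miscalculation, would be wrong.

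A reader might also infer that the 81% drops to 61% once the constant-hazard assumption is removed. It does not. The 61% belongs to another test and holds under a constant hazard too. The planned Wald test under a changing hazard can lie well above or below either figure.

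Nor do the documents show that the hazard falls. No cohort in them gives DFS, as the protocol defines it, at two times. The 76% row joins figures from different cohorts, so it is an illustration and not the trial's type I error.

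A 1-year comparison has limits of its own. Six 28-day cycles starting three to eight weeks after surgery end at about 27 to 32 weeks if there are no delays. One year then falls in the period of scans every 3 months, give or take a month (section 10), so status at 1 year depends on scan timing. DFS runs from surgery, yet the primary population contains only patients who go on to start adjuvant treatment. That restriction affects the hazard test as well.

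Finally, the event-count rule is stated as a failure condition and depends on accrual going to plan. Even when accrual does go to plan, the rule gives 2.5% and 55%, so the condition does not reconcile it with the Wald test.

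**Conclusion.** The point holds in this form: the plan names 1-year DFS, tests the hazard, and gives no test or power for the named endpoint that is free of the constant-hazard assumption. Power for a direct test is about 61% (n = 54, complete 1-year follow-up, one-sided 10%), against 81% for the hazard test if the hazard is constant. The effect on the planned test depends on how far the hazard departs from constant: success at a true 57% rises to about 24% for a modest assumed fall and 76% for a marked one, and success at a true 67.5% drops to about 40% if the benefit ends after year 1. The background makes a constant hazard doubtful but does not disprove it.

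The event-count conflict is a separate inconsistency, and it needs no departure from the plan's assumptions. Nothing here shows that a 1-year test must become primary; that would be a design choice, not a correction.

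**What to change.** Three changes to section 13, with no added patients:

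1. State that the tested hypothesis is the DFS hazard over full follow-up (.5621 versus .3935), and that the 81% is conditional on a constant hazard.
2. Make the Wald test the single deciding rule and remove the event-count rule, or keep that rule and state its own error rate and power (about 2.5% and 55%).
3. Prespecify a comparison of the Kaplan-Meier 1-year DFS with 57% as a sensitivity analysis. State its power (about 61% for 67.5%, 80% for about 71%) and note its dependence on scan timing near 1 year and on the restriction to patients who start adjuvant treatment.

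The cost is wording and one analysis, since the Kaplan-Meier estimate is already planned. The downside is a less favourable stated power for 1-year DFS. Making the 1-year test primary is optional: at n = 54 it means accepting about 61% power for 67.5%, and 81% by normal approximation would need about 100 patients.
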